1 R01 AT010598-01A1

Study Intervention Provided by:

NA

Sponsor of IND (IDE):

NA

Tool Revision History

Version Number: 1

Version Date: 03/11/2021

Summary of Revisions Made: NA

Version Number 2:

Version Date: 04/19/2021

Summary of Revisions Made:

- Protocol: Updated needle sizes; Added more info/clarification about ear seeds; Added information about topical Arnica cream to prevent bruising, for muscle pain, or in event of hematoma; Updated Inclusion/Exclusion criteria; Updated randomization process (REDCap OR Envelopes); Added a screening bubble in work flow diagram; Updated window for follow-ups from +/- 2 days to +/- 4 days; Added that acupuncturist will share Acupuncture After Care summary with AQ patients (with ear seeds and arnica info); Updated platform used for remote interviews from Zoom to “the audio only function of a HIPAA-compliant commercial tele-health platform (e.g. Zoom Health Professional or Doxy.me)”
- RCT Consent: Language about personal phone use/Twilio possibly/possibly not being available while in the ER; Updated ED to ER; Updated platform used for remote interviews from Zoom to “the audio only function of a HIPAA-compliant commercial tele-health platform (e.g. Zoom Health Professional or Doxy.me)”
- Study Information Sheet for both Provider and Patient: Updated platform used for remote interviews from Zoom to “the audio only function of a HIPAA-compliant commercial tele-health platform (e.g. Zoom Health Professional or Doxy.me).”; Updated ED to ER for patients

Version Number 3:

Version Date: 05/12/2021

Summary of Revisions Made:

- RCT Consent: Language about use of personal phones and Twilio messaging while in the ER has been removed from the protocol
- Updated the Co-investigators to include [name].

Version Number 4

Version Date: 05/21/2021

Summary of Revision Made:

- Study Design: included additional 15 pilot patients (5 per site) into the Sample Size and Population
- Protocol: removed UH specific research credentialing to allow study staff at Einstein Coordinating Center to be research credentialed at all three sites
- Outcomes: updated language for Primary Outcomes measures and Secondary Outcomes measures
- Inclusion Criteria: removed the 3V acuity level as this designation may not be standard at all sites, replaced with the standard 3 acuity level

- Exclusion Criteria: removal of 'Patient arriving via ambulance or skipping triage' exclusion criteria
- Study Enrollment Procedures: added language describing the patient's refusal to provide their phone number and email address as being a declination of participation in the study; added procedural language for distributing remuneration for completing the Qualitative Interview; added documentation language for tracking Qualitative Interview and number of phone call attempts
- RCT Consent: included the updated version of the Informed Consent that reflects the changes to the protocol listed above
- Provider Qualitative Interview Study Information Sheet: included the updated version of the provider information sheet that reflects the changes to the protocol listed above
- Patient Qualitative Interview Study Information Sheet: included the updated version of the patient information sheet that reflects the changes to the protocol listed above
- Updated the Executive, Steering and ED Physician and Site PI committees.
- Quality Assurance: added ACUITY QA Monthly Consent and Eligibility Data Review Tool and timing for review and completion of Eligibility Checklist

Version Number 5

Version Date: 08/19/2021

Summary of Revision Made:

- Study Enrollment Procedure: added the use of a pre-treatment flyer to the recruiting procedure
- Study Interventions: Arnica removed from the Acupuncture After Care sheet
- Study Procedures: the addition of satisfaction questions asked during the Post-Treatment assessment was noted in the Schedule of Evaluations with a detailed listing in the Follow-Up Visits section
- Study Enrollment Procedures: added study staff assessment of patient capacity to understand and sign documents prior to informed consent process and the addition of instruction to only continue with study activity after written consent is obtained to Recruitment Methods and Consent Process sections; and removal of clinical consent procedure
- Description of evaluation: added study staff assessment of patient capacity to understand and sign documents prior to informed consent process and the addition of instruction to only continue with study activity after written consent is obtained to Consenting Procedure section; and removal of clinical consent procedure
- Supplement/Appendices: replaced informed consents and information sheets with current documents
- Safety Assessment: removal of clinical consent procedure
- Data Management: added paper collection of PRO at 1-week and 4-week follow-ups

Version Number 6

Version Date: 12/09/2022

Summary of Revisions Made:

The objectives of this study are to: conduct a feasibility randomized control trial (RCT), to examine the feasibility of data collection in the RCT, develop a responsive acupuncture intervention and assess implementation and treatment outcomes in emergency departments associated with 3 BraveNet research sites. (UH Cleveland Medical Center ED (site 1), the Vanderbilt University Medical Center (VUMC) ED (site 2) and the Hillcrest University of California San Diego (UCSD) ED (site 3)). This study will include qualitative interviews and structured observation to assess feasibility of implementation.

Design and Outcomes

This is a multi-site single visit, un-blinded, feasibility randomized control trial of acupuncture in the ED.

Interventions and Duration

Acupuncture for pain management in the Emergency Department (ED) will be compared to usual care. The interventions will be administered during the ED visit. During that time, pre-, post- and discharge assessments will be administered. Follow up assessments will take place at one and four weeks post ED visit.

Sample Size and Population

The target population are adults presenting to the ED with acute non-emergent (musculoskeletal, back, pelvic, non-cardiac chest, abdominal, flank or head) pain ≥ 4 on a 0-10-point Numeric Rating Scale (NRS) due to non-penetrating injury. A total of 150 patients (50 patients per recruiting site) plus 15 pilot (5 per recruiting site) will be recruited study-wide.

Additionally, 30 (10/site) ED stakeholders, including providers (physicians, nurse practitioners, physician assistants, and registered nurses) and ED staff employed for at least one year including the study period, as well as acupuncturists who are employed or credentialed by one of the participating institutions to perform acupuncture in the emergency department as part of the study will be interviewed about their perspectives and experiences related to implementation of the acupuncture study in the ED.

Patients who are randomized to the acupuncture group will be contacted to participate in a brief qualitative interview about 3 weeks after their ED visit. The expectation is that up to 15 patient participants per site (n=45 total) will consent to the qualitative interviews about their experience of receiving acupuncture as part of the RCT.

STUDY OBJECTIVES

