3. STUDY DESIGN

Type/design of trial

This is a multi-site single visit, feasibility randomized control trial of acupuncture in the ED versus Usual Care.

Specific unit(s) of assignment and unit(s) of observation.

The unit of assignment is at the patient level. Specifically, acute pain patients enrolled in the ED will be randomly assigned to either acupuncture or usual care. The unit of observation is the patient.

Primary and secondary outcomes

The primary outcomes of the study will be the recruitment and retention patients into the study. The secondary outcomes will be the development of a responsive acupuncture intervention and assessment of implementation and treatment outcomes in emergency departments associated with 3 BraveNet research sites. Secondary outcomes will be assessed via qualitative interviews and structured observation to assess feasibility of implementation.

Study population and groups/arms including sample size

The study population are: (1) One hundred fifty (50/site) plus 15 pilot (5/site) adults presenting to the ED with acute non-emergent (musculoskeletal, back, pelvic, non-cardiac chest, abdominal, flank or head) pain ≥ 4 on a 0-10-point NRS due to non-penetrating injury. (2) Thirty ED stakeholders (10/site) including ED providers (physicians, nurse practitioners, physician assistants, and registered nurses) and ED staff employed at one of the three sites for at least one year including the study period as well as acupuncturists who are employed or credentialed by one of the participating institutions to perform acupuncture in the emergency department as part of the study. (3) Of the 150 subject noted above, patients who are randomized to the acupuncture group will be contacted to participate in a brief qualitative interview about 3 weeks after their ED visit. The expectation is that up to 15 patient participants per site will consent to the qualitative interviews about their experience of receiving acupuncture as part of the RCT. 4) Approximately 15 ACUITY study staff (n =~5/site);

Study locations

Randomized Control Trial

Subjects will be recruited as described above from: the UH Cleveland Medical Center ED (site 1), the VUMC ED (site 2) and the Hillcrest UCSD ED (site 3).

Structured Field Observation

About three, 6 hour shifts will be observed at each site during active patient recruitment and treatment.

Qualitative Interviews

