
Individuals who participate in the ED data collection procedures will be remunerated \$25 and those who complete the 1-week and 4-week follow-up assessments will be remunerated an additional \$25 per visit. Remuneration will happen within 45 days of the patients' ED stay. There is no current plan for recruitment or advertisement materials due to the nature of this study and immediate recruitment of subjects.

Qualitative Interviews:

Patient Interview Recruitment Methods: Patients who participate in the RCT will have been informed as part of the informed consent process that they may be contacted to participate in a qualitative interview if they are assigned to the acupuncture group, and they will have been given the option to opt out of being contacted for the interview. Study staff from the Einstein Coordinating Center, who will be

research credentialed, will contact the patients in the acupuncture group via email and/or phone within a week of their ED visit to schedule the interview and to share the study information sheet for them to review. Participant contact with the research staff for qualitative interviews will be documented in REDCap with up to 5 attempts to schedule the qualitative interview.

ACUITY Study Staff Interview Recruitment Methods will be scheduled to occur either in person in a private room, when possible, or remotely via a HIPAA-compliant commercial tele-health platform: (e.g. Zoom Health Professional or Doxy.me) by research credentialed study staff from Einstein Coordinating Center. Study staff will have the choice of audio or video interview. Einstein Coordinating Center staff conducting the interviews remotely will be in a private room when interviewing the participants. A stamped copy of the informed consent document will be shared with the participant before the scheduled informed consent process, and the consent will be signed and dated by the participant and by the Einstein staff conducting the informed consent process, either in person or electronically using UH REDCap, before beginning the interview. The interviews will take approximately 45 minutes to complete and will be recorded and transcribed. A short demographics survey will be securely emailed to the participant during the interview via [contact] email address and will be completed and emailed back before the conclusion of the interview.

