Provider Interview Recruitment Methods: We will use staff rosters to identify physicians, nurse practitioners, physician assistants, nurses and ED staff who have been employed by in the ED at one of the three sites during the data collection period and to identify ACUITY study staff and the acupuncturists performing the intervention as part of the study. Research Credentialed study staff from the Einstein Coordinating Center or local study staff who have been trained to conduct the qualitative interviews will contact these providers and staff, whether in person, or by email, followed by phone, to invite them to participate and to share study information sheet for them to review.

All individuals who participate in the qualitative interviews will be remunerated \$25 within 30 days of the interview. The qualitative interview team from Einstein Coordinating Center will inform respective site study staff once a patient's qualitative interview is complete. Site study staff will contact the patient with the e-gift card code or mail a physical gift card and will mark in REDCap when this was completed.

Documentation of reasons for ineligibility.

We will maintain a screening and enrollment log to document ineligibility reasons and for non-participation of eligible candidates.

Consent Process

Randomized Control Trial Consent Process

The consent process will occur after the patient has gone through the triage process and been assigned to a room within the ED. The consent process will be conducted by dedicated research staff (SC or RA) that have been trained in obtaining informed consent. The status and location of the patient will be monitored by research staff using the EHR to ensure the patient is approached at an appropriate time.

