Patient Interview Consent Process: Patients who are consented to participate in the RCT will be informed as part of that consent process that if they are randomized to receive acupuncture as part of the study, we may approach them to invite them to participate in an interview. The consent form will include language informing the patient that the interview will take place via the audio-only function of a HIPAA-compliant commercial tele-health platform: (e.g. Zoom Health Professional or Doxy.me) and will be recorded and transcribed. There will also be an option for the participant to opt out of being contacted for the interview. Research credentialed study staff at the Einstein Coordinating Center will contact participants randomized to the acupuncture arm within a week after their ED visit to schedule the interview and to share the study information sheet to review. Participant contact with the research staff for qualitative interviews will be documented in REDCap with up to 5 attempts to schedule the qualitative interview. At the time of the interview, the interviewer will review the study information sheet with the patient. This document will explain that the interview will be recorded and transcribed, and will reiterate the voluntariness of participation. The document will explain that if the participant continues with the interview, they are agreeing that they have read the information and that they voluntarily agree to participate and to be recorded for transcription purposes.

Provider Interview Consent Process: Identified providers/staff and study staff will be contacted by research credentialed study staff at The Einstein Coordinating Center, either in person during their site visit or via email followed by phone, and invited to participate in the interview. They will schedule the interview at the providers' convenience. A study information sheet will be shared via email with the provider ahead of the interview, and will be reviewed at the beginning of the scheduled interview. This document will explain that the interview will be recorded and transcribed, and will reiterate the voluntariness of participation. The document will explain that if the participant continues with the interview, they are agreeing that they have read the information and that they voluntarily agree to participate and to be recorded and transcribed.

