6.2.5 Completion/Final Evaluation

Four Week Follow-Up Assessment Visit

4 week follow-up Assessment (Follow-up) will be obtained via REDCap based text message or email (or phone call from research staff) at 4 week (+/- 4 days) of patient's ED discharge for both arms. To maintain assessor blinding, any 4-week phone calls (if needed) will be conducted by a research staff (SC or RA) who did not interact with the patient during their study participation in the ED.

- Pain Assessment (Post) using a 0-10 NRS
- Anxiety scores using a 0-10 NRS
- Satisfaction and will be measured through brief questions. All participants will be asked to

answer:

- "How satisfied are you with how your pain was managed during your ED visit" on the 5-point Likert scale.
- "Overall how satisfied are you with your treatment during your ED visit?" on the same Likert Scale.
- Pain medications utilized from ED Discharge to 4 weeks after discharge will be obtained from patients via phone call, email, or text messaging via the secure REDCap electronic data collection tool.

Early Termination

The study doctor or the sponsor can stop a subject's participation at any time without their consent for the following reasons:

- If it appears to be medically harmful to them;
- If they fail to follow directions for participating in the study;
- If it is discovered that they do not meet the study requirements;
- If the study is canceled; or
- For administrative reasons, including competitive enrollment (e.g. the target number of subjects has entered the study.)
- If the patient's clinical condition worsens emergently as determined by the ED physician/clinician.

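### Interview contact goes only to the acupuncture arm and comes before follow-up is complete, so 1-week and 4-week retention by arm may partly reflect unequal contact

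*Combined protocol and SAP*

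**What the plan says.** - **Outcome.** Section 3 states: "The primary outcomes of the study will be the recruitment and retention patients into the study". Sections 9.5, 9.5.1 and 9.6 (Aim 2a) assess retention or loss to follow-up at each data collection point, overall, by site and across the study arms.
- **Who is interviewed, and when.** The Précis says that patients "randomized to the acupuncture group will be contacted to participate in a brief qualitative interview about 3 weeks after their ED visit", and Section 3 repeats this. Among patients, Section 4.1 admits to interview only those who received acupuncture. Up to 15 per site (45 in total) are expected.
- **Scheduling contact.** In Section 4.3 (Patient Interview Recruitment Methods), Coordinating Center staff "will contact the patients in the acupuncture group via email and/or phone within a week of their ED visit to schedule the interview", "with up to 5 attempts to schedule the qualitative interview". The Patient Interview Consent Process says the same: staff "will contact participants randomized to the acupuncture arm within a week after their ED visit to schedule the interview". Patients may opt out of this contact.
- **Payment.** The interview pays $25, due within 30 days of the interview. Site staff then send the gift card and "will mark in REDCap when this was completed". Payment for the ED visit and the two follow-ups has no arm distinction: "Remuneration will happen within 45 days of the" ED stay.
- **Follow-up windows.** The 1-week assessment is due at 1 week ±4 days (Section 6.2.4). The 4-week assessment "will be obtained via REDCap based text message or email (or phone call from research staff) at 4 week (+/- 4 days") of discharge, in both arms (Section 6.2.5).

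No section gives usual care matching contact, places the interview after the 4-week form, or says how unequal contact will be handled when retention is reported.

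**The concern.** The trial exists to learn whether its procedures, follow-up included, will work in a larger study. Late follow-up was the pilot RCT's weak point: Section 2.2 reports about 35% completion at 30 days and concludes that new follow-up methods are needed. Here one arm gets up to five extra contact attempts, a conversation about its ED experience and the promise of $25 before the last follow-up form is due. The other arm gets none of these.

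An arm difference in 1-week or 4-week retention could therefore reflect the interview program rather than the treatment or the follow-up method. The overall rate carries half of any such effect, and a definitive trial may not include these interviews. The direction is open: contact may keep patients engaged, or it may add burden.

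**Working it through.** **1. Timing (day 0 = ED visit).**
- 1-week window: 7 ± 4 = days 3 to 11. Scheduling contact begins by about day 7, so it can fall inside this window.
- 4-week window: 28 ± 4 = days 24 to 32. The planned interview at about day 21 precedes the form by 24 - 21 = 3 to 32 - 21 = 11 days. The interview date is approximate, so some interviews may run later.
- Interview payment: as late as 21 + 30 = day 51. Only the promise of payment is sure to come before the form.

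**2. The plan's own figures.**
- Pilot 30-day completion: 16/46 = 34.8%, matching the stated 35%. No 4-week retention target is given for this trial.
- Definitive-trial inflation (Section 9.2): 255/0.78 = 326.9, so 327 per arm and 654 in total, as stated. The 78% is post-treatment retention, which is collected before any interview contact.

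**3. Share interviewed.** About 150/2 = 75 patients per arm (equal allocation assumed from the permuted blocks of 2 and 4). The ceiling is 45/75 = 60%. Because 15 per site is an upper expectation, patients may opt out and sampling stops at saturation (Section 9.6), 30/75 = 40% and 15/75 = 20% are also shown.

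**4. Possible shift in 4-week retention.** The documents give no effect of interview contact on completion, so the change *d* among interviewed patients is an assumption.

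Arm gap = share × *d*. Overall shift = gap/2. Each cell shows gap / overall shift, in percentage points.

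| Share interviewed | *d* = -10 | *d* = 0 | *d* = +10 | *d* = +20 |
|---|---|---|---|---|
| 60% | -6 / -3 | 0 / 0 | 6 / 3 | 12 / 6 |
| 40% | -4 / -2 | 0 / 0 | 4 / 2 | 8 / 4 |
| 20% | -2 / -1 | 0 / 0 | 2 / 1 | 4 / 2 |

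The table counts the interview only. Scheduling contact without an interview, which is the route by which 1-week retention is exposed, is not counted.

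**5. Could the trial see it?** The 95% half-width of an arm difference is 1.96 × √(2p(1 - p)/75):
- p = 0.35: 15.3 points
- p = 0.60: 15.7 points
- p = 0.78: 13.3 points

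Every gap in the table is smaller than this. Power to detect a 6-point gap with 75 per arm is about 11% to 15% for usual-care retention between 35% and 78%.

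**The case against.** **No stated decision turns on these figures.** There is no retention threshold or go/no-go rule, and by-arm retention is one descriptive breakdown among several. This stands, and it is why the point is an improvement rather than a flaw that undermines the trial.

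**The effect is wholly assumed.** Patients who agree to an interview are probably easier to reach already and have less room to gain, so the +12 corner needs both the 60% ceiling and a 20-point gain. This also stands. But data that could not reveal the effect afterwards are a reason to prevent it by timing.

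**Interviewing only acupuncture recipients follows from the question asked.** True. The point concerns when they are contacted, not who is interviewed.

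**Delay could cost interviewees.** Reaching 15 of about 25 acupuncture patients per site needs 60%. At the pilot's 34.8%, about 25 × 0.348 = 8.7 per site would be reached. That rate came from 30-day phone follow-up, and a day-21 interview would probably face similar reach, so most of this risk is not caused by the delay.

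**Stronger readings that a reader might infer.** None of these is supported:
- *That acupuncture retention is inflated.* Neither the direction nor the existence of an effect is documented.
- *That interview money reaches patients before the 4-week form.* It may arrive well after it.
- *That the 654 is compromised.* It uses post-treatment retention.
- *That 4-week pain or anxiety comparisons are biased.* The documents do not state such a comparison by arm.

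**Conclusion.** The point holds as a design weakness that is cheap to remove. Only the acupuncture arm receives interview contact. That contact can overlap the 1-week window, and both contact and the planned interview precede the 4-week window. Retention at 1 and 4 weeks by arm, and to half that extent overall, may therefore reflect contact that usual care does not get.

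The size is unknown. The illustrative range for 4 weeks is an arm gap of -6 to +12 points and an overall shift of -3 to +6. It rests on about 75 patients per arm, at most 45 interviewed, and an assumed change of -10 to +20 points among them. The true effect may be zero, and this trial could not separate it from chance. Post-treatment and ED-discharge retention are unaffected.

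**What to change.** **If interviews have not begun.** Start interview scheduling and interviews only when the patient's 4-week form is complete or its window has closed (day 32). Approach patients who did not complete the form on the same terms as those who did, so that the purposive sample in Section 9.6 is not tilted toward retained patients. Change the scheduling-contact timing in Section 4.3 (both places) and the interview timing in the Précis and Section 3. Make the statement in Section 3 that patients are enrolled for about 4 weeks consistent with this, along with any matching wording in the patient information sheet.

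**Cost.** Wording edits; interviews about 3 to 11 days later plus scheduling time; somewhat longer recall of the ED visit; and possibly fewer interviewees.

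**If interviews have begun.** State beside the 1-week and 4-week retention results that the arm comparison may reflect unequal contact. Do not rely on a breakdown by contact status, which is nearly the same as arm, or by interview completion, which is self-selected after randomization. For the same reason, do not drop interviewed patients. Do not take usual-care retention alone as the planning figure either: in an un-blinded trial the arms may differ in retention for other reasons.
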